6.0 Reporting

Unanticipated problems

Study staff will report any unanticipated problems to the PI and study coordinator via encrypted e-mail and/or phone call. All problems will be documented using internal logs saved locally behind the VA firewall.

Unanticipated problems that do not significantly impact the experience of participants or result in a deviation from the study protocol will be noted and provided to the IRB in annual report. Recurring problems will form the basis for amendments in order to improve Veteran and family member experiences, improve data quality, and/or minimize the impact on clinical care activities within referring clinics.

Per IRB regulations, problems or events resulting in a deviation from the study protocol (e.g., emergency hospitalization to address suicidal behaviors) will be reported to the PI within 24 hours and to the IRB in 48 hours using required IRB forms.

Adverse events

All internal serious adverse event reports will be sent via encrypted e-mail to the PI and Study Coordinator. Copies of all SAE reports (both IRB forms and internal study forms) will be saved locally behind the VA firewall. No paper copies will be saved. Adverse events will include all suicide attempts, reports of new intimate partner violence behaviors (of any severity) after the initial screening, and occurrences of imminent risk. Per IRB regulations, any serious adverse event, any event resulting in a deviation from the study protocol (e.g., emergency hospitalization to address suicidal behaviors) or death will be reported to the PI within 24 hours and to the IRB in 48 hours. This will be completed in order to assess significance and determine an appropriate response. Adverse events that involve temporary distress will be noted by interviewers and provided to the IRB in an annual report.

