In order to accommodate Veteran preferences/comfort as well as respond to participants' accessibility/health/safety needs, this baseline may be conducted in person or remotely. In a remote session, research staff will mail questionnaires and consent forms to the participant ahead of the session and then discuss the materials with that participant over the phone/VVC. Participants will then be able to return signed forms through self-addressed, pre-stamped envelopes to the VA. To maximize accessibility for participants with reading or writing difficulties, they will have the option to (1) complete the questionnaire packet to mail to staff in pre-stamped envelopes; or (2) use the packet as a reference when completing questionnaires verbally with the staff. Finally, the interviews will be conducted directly over the remote platform (phone/verbally).

By conducting the baseline separately, we will be able to individually screen partners for risk factors and exclusion criteria (e.g., severe IPV, recent suicidal ideation with intent) and initiate appropriate safety planning one-on-one with that partner. This reflects VA couple therapy guidelines as well as recommendations for telehealth with couples, where appropriateness for therapy is evaluated using separate individual sessions with each partner and safety planning is conducted individually to maximize safety and privacy.

Intervention.

The first session can be scheduled as soon as one day after the second partner completes the baseline. Sessions are expected to be scheduled every 1-2 weeks and will ideally occur

over a 30-day window. Treatment will be based on the BRC manual developed for Air Force primary care with modifications noted below (*Doc#18*). In order to protect Veteran health/safety and accommodate Veteran preferences/comfort, couples may also conduct any and all the joint BRC sessions as a remote session (i.e., by VVC/phone). Prior to each session, participants will complete relevant sections of the Intervention Packet (*Doc#17*) including the "Relationship Checkup (RC) Questionnaire," a list of relationship strengths and concerns used to focus the discussion. For Veterans participating remotely, RC questionnaire packets will be mailed to the couple along with separate self-addressed, pre-stamped envelopes for each partner.

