Follow-up Semi-structured Interview (Doc#20). After the final treatment session, partners will be asked to schedule separate follow-up interviews with study staff between within 30 days of the final treatment session. Interview will consist of an open-ended treatment evaluation, suicide ideation assessment, and IPV assessment (modified to a 1-month timescale). As above, this can be completed remotely or in-person based on participant convenience

After completing the final interview and questionnaire, participants will be thanked, final payments will be made, and no further contacts will be scheduled. Participants who request further treatment will have any requested consultations scheduled. Participants that share any risk concerns (i.e., new violence over the prior month; any ideation with intent over the prior month) will be immediately referred to appropriate resources for follow-up.

Risk benefit analysis

Anticipated benefit. Participants may experience indirect benefits of study participation. As part of the check-up process, participants will be thoroughly screened for individual mental health concerns and relationship concerns and will be offered treatment recommendations and referrals, which may lead to concerns being addressed in treatment.

Prior research in civilian couples and active duty Airmen suggest that participating in the BRC intervention sessions may lead to direct improvements for relationship quality for some couples, however we cannot guarantee that any direct benefit will be experienced by the couples in our study.

Dissemination of the findings from the study will contribute to the extant literature, provide data to guide a larger trial, and may contribute to knowledge about ways to better support well-Veteran relationships.

Population risk. The purpose of this project is to pilot a brief intervention with Veterans screening positive for known suicide risk factors (i.e., depression, alcohol use, PTSD, suicide ideation) and known IPV risk factors (i.e., relationship distress, alcohol use, PTSD). Thus, participants will be at a somewhat elevated risk for suicidal crises, intimate partner violence, and other negative outcomes.

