5.4 Inclusion/Exclusion Criteria

List of criteria for inclusion

- 1) Both partners must be age 18 or over
- 2) Both partners must demonstrate sufficient knowledge of English and cognitive capacity to understand the study through comprehension of consent questions
- 3) Both partners must self-identify as "in a committed relationship" with their partner for at least 6-months.
 - *Note:* Eligibility will NOT be based on marital/cohabitation status or sexual orientation to remain consistent with VA priorities of offering inclusive family services.
- 4) At least one partner must report at least mild relationship distress on a satisfaction screen (CSI-4<13.5)
- 5) At least one partner must have Veteran status
- 6) The Veteran partner must screen positive on at least one PC-Screen (i.e., PHQ-2 ≥3; PHQi9≥1; AUDIT-C≥5; OR PC-PTSD-5≥4)

List of criteria for exclusion:

- Either partner reports that they are engaged in ongoing couple or family therapy (via brief questions during Telephone Screen).
 Note: Any new couple/family therapy scheduled *after* screening will not impact eligibility and will be evaluated as an outcome.
- 2) Either partner reports severe intimate partner violence in the last year (via semi-structured interview during the Baseline session).
- 3) Either partner reports experiencing suicidal intent / attempts in the last month (via C-SSRS in Baseline session).
 - *Note:* Participants will NOT be excluded based on suicidal ideation or plan alone.
- 4) Either partner experiences current psychosis (via chart review, presentation during session, or MINI psychosis scale).
- 5) Either partner experiences current mania (via chart review, presentation during session, or MINI mania scale).

All staff will be trained in the semi-structured IPV interview, C-SSRS, P4, and MINI psychosis and mania scales to be used at any time they are concerned about individual functioning during either in-person sessions or phone sessions. Veteran charts will be reviewed prior to any Veteran-participants' to check for any indications of hospitalization or records flag. Results will be discussed with Drs. [name] or [name], licensed psychologists who will integrate findings to determine whether exclusion criteria are met.

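### The adverse-event list does not name suicidal ideation with intent arising after baseline, so intent that is not judged imminent at contact may go unrecorded as an adverse event

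*Combined protocol and SAP*

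**What the plan says.** Four places bear on this point.

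- **Section 5.1, Baseline.** Partners are seen separately so that each can be screened for "risk factors and exclusion criteria (e.g., severe IPV, recent suicidal ideation with intent".
- **Section 5.4, exclusion 3.** Either partner is excluded for suicidal intent or attempts in the last month, assessed "via C-SSRS in Baseline session". A note adds: "Participants will NOT be excluded based on suicidal ideation or plan alone". Intent is thus the protocol's own dividing line.
- **Section 5.1, Follow-up assessment.** The text reads "Participants that share any risk concerns (i.e., new violence over the prior month; any ideation with" and continues with intent over the prior month. Such participants "will be immediately referred to appropriate resources for follow-up". Imminence is not a condition, and adverse-event recording is not mentioned.
- **Section 6.0, Adverse events.** These "will include all suicide attempts, reports of new intimate partner violence behaviors (of any severity) after the initial screening, and occurrences of imminent risk". The same paragraph sets expedited reporting for serious events, deaths and events that cause a protocol deviation. It also sends adverse events involving temporary distress to the IRB once a year.

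Table 1 in Section 5.5 schedules the C-SSRS for last-month ideation at baseline and post-treatment, and the P4 screener as needed at every stage. The Abstract says there is no data safety monitoring board; safety is monitored by the principal investigator, the IRB and the compliance office.

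**The concern.** The protocol uses intent as a safety threshold on entry and again at follow-up, but the reporting section does not carry it over. New partner violence of the mildest kind is a named adverse event. New suicidal intent is not, unless someone judges the risk imminent.

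This matters more here than in most pilots. The study is motivated by suicide prevention. Section 5.1 accepts that participants are at somewhat elevated risk of suicidal crisis and that joint sessions may add stress or conflict. Without a monitoring board, adverse-event reports are a main route by which the IRB learns of possible harm. The log could show no suicide-related event while the post-treatment C-SSRS holds one or more reports of intent.

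**Working it through.** The plan states no figure to reproduce. The check is a comparison of wording.

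**Step 1. Set the lists side by side.**

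| Event | Exclusions (5.4) | Follow-up risk concern (5.1) | Adverse-event list (6.0) |
|---|---|---|---|
| Suicide attempt | Yes, last month | Not in this parenthesis | Named, all |
| Ideation with intent | Yes, last month | Yes, prior month | **Not named** |
| Partner violence | Severe only, last year | Yes, new, prior month | Named, new, any severity |
| Imminent risk | Not used | Not used | Named, not defined |

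Of the two elements of exclusion 3, attempts are named in 6.0 and intent is not. Of the two follow-up risk concerns, violence is named and intent is not.

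**Step 2. Ask whether imminent risk closes the gap.** Section 5.1 uses the term as a trigger for emergency procedures during a contact. It also has a separate higher-risk category with its own safety plan, and it ties neither level to intent. Three cases follow.

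- Intent current at contact and judged imminent: a named adverse event.
- Intent current but not judged imminent: not named, and the classification depends on the rater.
- Intent within the past month, resolved by the interview: neither an attempt nor, on an ordinary reading, imminent risk. Referral follows; an adverse-event record need not.

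**Step 3. Ask whether such intent is new since baseline.** Exclusion 3 clears the month before baseline. Study activities take from one month to three months after baseline, and the post-treatment C-SSRS looks back one month. The look-back therefore falls after baseline or, at the edge, overlaps a month already cleared. An enrolled participant who reports last-month intent at that point has had it since baseline, provided the baseline answer was accurate. It need not be a first episode: intent two months before baseline does not exclude.

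**Step 4. Size.** Section 5.6 projects 75% retention: 20 × 0.75 = 15 couples, or 15 × 2 = 30 people. The documents give no rate of emergent intent. Purely as assumptions, with one common rate p and independent participants, the chance of at least one case is 1 − (1 − p)^30:

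- p = 2%: 45%
- p = 5%: 79%
- p = 10%: 96%

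These values are illustrative and are not evidence of size. A common p is doubtful, because only the Veteran must screen positive, and partners in a couple are unlikely to be independent.

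**The case against.** Several stronger readings are tempting, and the documents do not support them.

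- **That intent cannot be counted as an adverse event.** The list says what adverse events will include; it is not closed. Section 6.0 also covers temporary distress, unanticipated problems, serious events and events causing a deviation, and Section 5.7 sends safety withdrawals to the same reporting rules. This stands, so the claim is only that intent is not named and may be missed. These routes are weak substitutes: filing intent under temporary distress would hide its nature and hold it for an annual report.
- **That Sections 5.1 and 6.0 contradict each other.** One lists triggers for referral, the other events for reporting, and nothing requires them to match. This also stands. The point is an unexplained omission.
- **That intent would go undetected or unanswered.** It would not at follow-up: the C-SSRS is scheduled and immediate referral is required.
- **That the RCT team would be misled on safety.** The remark in Section 5.6 about tolerability and safety concerns exploratory outcome analyses. The team would hold the C-SSRS data whatever the log shows. However, the planned Cohen's d estimates would not yield a count of people with intent, and the IRB works from reports.
- **That post-baseline intent is caused by treatment.** A single-arm study in an at-risk population cannot show this. Recurrence is possible.

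The most forceful objection is that staff may class all current intent as imminent, which would leave only resolved intent outside the list. That narrows the clear gap. It also shows that counting turns on an undefined term.

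**Conclusion.** The point holds in a limited form. Section 6.0 does not name suicidal ideation with intent, although the protocol treats it as a threshold in Sections 5.1 and 5.4. Post-baseline intent that is not judged imminent is measured and referred at follow-up but may not enter the adverse-event log. The clearest instance is intent within the past month, reported at the post-treatment interview and since resolved. Suicide-related events could be under-counted in what the IRB sees.

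The size is unknown. The conclusion rests on the wording of the three sections and on the absence of a definition of imminent risk, not on any assumed event rate. Reading post-treatment reports as new since baseline also assumes accurate answers at baseline.

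**What to change.** Reconcile Sections 5.1, 5.4 and 6.0 as follows.

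1. Add to the adverse-event list in Section 6.0: *suicidal ideation with intent occurring after the baseline assessment, whether or not risk is judged imminent at the time of contact*. The word *occurring* matters. Table 1 asks about lifetime ideation again at post-treatment, so a rule based on when intent is first reported would count late disclosure of pre-study intent.
2. Code it from the last-month C-SSRS at post-treatment and from any C-SSRS or P4 given during treatment. Because the study can run three months from baseline and the look-back is one month, up to about 3 − 1 = 2 months may be covered only by those as-needed assessments. A report of results should say so.
3. State what imminent risk means for reporting purposes, so that classification does not vary by rater.

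This changes record-keeping only. It adds no assessment and alters no clinical procedure. The cost is a few lines in Section 6.0, a few more forms and possibly a slightly higher adverse-event count.

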7.0 Privacy and Confidentiality

Confidentiality and limits of confidentiality. All participants will be instructed in the informed consent and at the initiation of treatment the limits of confidentiality and the fact that if we feel they may be in imminent danger of harming themselves or others that we will involve other medical providers/emergency staff to protect their safety. Additionally, if we are concerned about the safety of a child, we will inform relevant authorities consistent with VA law. Participants will further be informed that the Veteran's Baseline assessment, treatment sessions, and follow-up contacts will be documented in the medical record of the Veteran's charts using study participation notes.

Documentation in the Veteran's chart. Study participation notes will notify other VA providers only that the Veteran is participating in the study and receiving an intervention for relationship concerns (see *CPRS Note Templates, Doc#31*). No other components will be documented unless clinically necessary.

Creation of Collateral Charts. Contacts with non-Veteran partners during the couples sessions will generally be documented VETERAN'S chart only. Collateral charts will NOT be routinely created. In situations when non-Veteran partners indicate a personal problem or concern (e.g., imminent suicidality, imminent homicidality, severe intimate partner violence, medical event during session) that is serious enough to warrant its own disposition and documentation, we will follow established clinic procedures for creating a collateral chart. This is consistent with the approach used in couples-therapy research in Austin VA, documentation of partner contacts as part of collateral assessments during VA IPV programs, and VA guidance for family clinics (e.g., VHA Directive 1603.04 Appendix A.6, "Documentation of Services to Relatives as Part of Family Services").

Documentation when Both Partners have Separate Charts. In couples where both partners already have separate charts (e.g., both partners are Veterans; partner already has collateral chart due to already existing receipt of services through the VA) each partner's participation will be documented in their OWN respective medical record using the note template. To maximize privacy, notes are designed to minimally describe the other partner's experience. The only exception is noting that the partner has completed the Baseline and that the couple will be enrolled in the intervention.

Data flow and data storage. Recorded interviews and intervention sessions and all informed consent forms will contain identifying information. In order to maximize confidentiality, signed forms (e.g., consent forms; signed acknowledgment of privacy practices) will be stored in separate double-locked files from other study materials (e.g., questionnaire data; digital recorders). As noted in our Data Transport memo (*Doc#23*) locked courier bags will be used to transport any sensitive study information (e.g., consents, audio recorders) outside VA property from ROPC to storage in the CoE. To maximize confidentiality, identifiable information will be transported in separate locked bags from de-identified questionnaires.

Digital recordings of interviews will be recorded under the unique participant ID number (no names will be used to label these recordings). Recordings on digital recorders, transported from interview sites in locked bags, will be promptly uploaded to the local site's secure server and deleted off the digital recorder. This action will be logged in the local site's audio recorder file deletion log. Recordings made using VA software will be saved directly to the secure server. Any identifiable paper data will be stored in two separate locked file cabinets (one for informed consents and the other for paper questionnaire data) in the offices of the CoE. After a participant completes the study, any identifiers will be removed from the paper questionnaire data and will be replaced with their numeric identifier.

CoE servers are password protected and has regular backups, and to which only IRB approved VA research personnel have access. Should any identifiable information need to be

shared between research sites, research teams will utilize a secure, SharePoint site or electronic communication with PKI encryption. Data will not be stored directly onto the hard drive of a PC or laptop.

VINCI will be used for the long-term storage of study data. VINCI is a major informatics initiative of the Department of Veterans Affairs (VA) that provides a secure, central analytic platform for performing research and supporting clinical operations activities. It is a partnership between the VA Office of Information Technology (OI&T) and the VHA Office of Research and Development (VHA ORD). VINCI includes a cluster of servers for securely hosting suites of databases integrated from select national VA data sources. VINCI servers for data, applications and virtual sessions are physically located at the VA Austin Information Technology Center (AITC), located in Austin, Texas. This secure enclave with 105 high-performance servers and 1.5 petabytes of high-speed data storage has multiple layers of security and disaster recovery to prevent data loss. VINCI is equipped with secure download and upload utilities which will be used to move PII and PHI between VINCI and other VA systems. Questionnaire Data analysis will occur in the VINCI framework using approved software.

Read and write access to VA servers, VINCI project files, or SharePoint will be restricted to IRB approved VA research personnel. When study personnel are no longer part of the research team, we will terminate data access using appropriate procedures.

Data will not be disclosed to any other person or entity except as required by law for authorized oversight of the research study.

Data disposition. Study data will be kept in accordance with the Department of Veterans Affairs Record Control Schedule 10-1 (RCS 10-1). If and when it is deemed appropriate to destroy data according to RCS 10-1, we will consult with the ISO on current standards and process for destruction. Storage and transfer of any Personally Identifiable Information (PII) or Protected Health Information (PHI) must be done in accordance with applicable VA and VHA policies and directives, state and federal regulations, and applicable statutes including the Health Insurance Portability and Accountability Act (HIPAA). Unless explicitly requested and approved by data stewards, all sensitive patient data must remain on VINCI project servers and only aggregate data without PII / PHI may be transferred from VINCI.

Publication and Reports. All data will only be used for scientific research purposes. No personnel will directly (e.g., through name or recognizable audio) or indirectly identify any individual patient or subject in any report of such research or otherwise disclose patient or subject identities in any manner.

